5 STUDY ENROLLMENT AND WITHDRAWAL

5.1 INCLUSION CRITERIA

Screening for eligible subjects will be performed within 28 days before study entry unless stated otherwise in the Schedule of Events. Prior to study entry, each potential subject must satisfy all of the following inclusion criteria. Obtaining pathology samples is not required prior to enrollment, but confirmation of availability is required prior to enrollment.

Disease Related

1. Subjects with histologically documented Follicular lymphoma CD20+ (Grade 1, 2 or 3a) *OR* Marginal zone lymphoma CD20+ (nodal, extranodal or splenic) according to World Health Organization (WHO) criteria.
2. Ann Arbor Stage II (Non-contiguous), III or IV disease
3. Patients must have a whole body or limited whole body PET/CT scan performed within 42 days prior to registration. CT portion of PET/CT will be done with contrast based on current NCCN guidelines unless patient has borderline renal function or allergic to contrast dye.
4. Patients must have bone marrow biopsy performed within 6 months prior to registration
5. Measurable node must have an LDi greater than 1.5 cms. In the absence of nodal lesions, measurable extranodal disease should have an LDi greater than 1 cm. In patients with Splenic Marginal Zone lymphoma, in the absence of nodal lesions, spleen size should be over 14 cms with evidence of lymphoma in the bone marrow biopsy.
6. For low tumor burden lymphomas (as determined by GELF criteria)⁷: Include patients diagnosed within 2 years of diagnosis. Low tumor burden patients diagnosed more than 2

years from study entry will be allowed provided patients have documented progression.

Prior Therapy Criteria

1. Patients must be untreated advanced stage disease (Stage III or Stage IV) or Stage II (non-contiguous). (Exception: Involved field or involved site radiation given for localized diagnosis is not considered a line of therapy).

Clinical/Laboratory Criteria

1. Patients must be ≥ 18 years of age and be able to swallow and retain oral medication
2. ECOG performance status of 0-2
3. Patients must have adequate bone marrow function as evidenced by ANC $\geq 1000/\mu\text{L}$ and platelets $\geq 50,000\mu\text{L}$ and Hb $\geq 8\text{g/dL}$ within 28 days prior to registration unsupported by growth factors.
4. Serum creatinine $< 2.0 \text{ mg/dL}$ or calculated creatinine clearance (CrCl) $> 45 \text{ mL/min}$

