5. Patients must have adequate hepatic function obtained within 28 days prior to registration and documented by all of the following:
 - Total bilirubin $\leq 1.5 \times \text{IULN}$ ($\leq 5 \times \text{IULN}$ if secondary to lymphoma, Gilbert's syndrome, or medication related)
 - Direct bilirubin $\leq 1.5 \times \text{IULN}$ ($\leq 5 \times \text{IULN}$ if secondary to lymphoma)
 - AST and ALT $\leq 2.5 \times \text{IULN}$ ($\leq 5 \times \text{IULN}$ secondary to lymphoma)
6. Patients must be willing to receive *Pneumocystis jirovecii* prophylaxis with sulfamethoxazole/trimethoprim, dapsone, and atovaquone or inhaled pentamidine, if they initiate combination umbralisib plus ublituximab (not for single agent ublituximab)
7. Patients must have a complete history and physical examination within 28 days prior to registration
8. Patients with follicular lymphoma must have the following components of Follicular Lymphoma International Prognostic Index (FLIPI) available from diagnosis, and collected again at time of registration:
 - Age
 - LDH
 - Number of nodal groups involved
 - Serum or plasma hemoglobin
 - Ann Arbor StageAdditionally, patients must have beta₂-microglobulin collected at time of registration and response assessment.
9. Female subjects of reproductive potential must have a negative serum pregnancy test within 3 days prior to treatment start date. Female subjects who are of non-reproductive potential (i.e., post-menopausal by history - no menses for ≥ 1 year; OR history of hysterectomy; OR history of bilateral tubal ligation; OR history of bilateral oophorectomy at least six weeks ago) are exempt from pregnancy testing. In the case of oophorectomy alone,

only when the reproductive status of the woman has been confirmed by follow up hormone level assessment is she considered not of child bearing potential.

10. Male and female subjects of reproductive potential who agree to use both a highly effective method of birth control (e.g., implants, injectables, combined oral contraceptives, some intrauterine devices [IUDs], complete abstinence, or sterilized partner) and a barrier method (e.g., condoms, cervical ring, sponge, etc.) during the period of therapy.

The following are UNACCEPTABLE forms of contraception for females of childbearing potential:

- natural family planning (rhythm method)
- breastfeeding
- fertility awareness
- withdrawal

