Trial Period	Screening	C1 (Single Agent Induction) ²⁹				End of Induction	Combination Treatment (Patients with < CR)				EOT ^{16 &18}	Follow-up (On Single Agent OR Combination Treatment)			
		C1 ¹⁵	C2		C3- 12										
Treatment Cycle/Title	-28 to D0	D1 ⁹	D8	D15	D22	4 weeks post Induction Tx	8 Weeks Post Induction Tx	D1	D8 and D15	D1	D15	D1	D+4 weeks post combination Tx	12 Weeks Post Completion of Combination Tx	3 M 6, 9, 12, 15, 18, 21 & 24 M 30 M+ Q6M Yrs. 2-5
Scheduling Window		± 1D			+7 days	± 7D	± 2D				+7 days	± 14D	± 28D		
Urinalysis ²⁴	X					X							X		
HIV Testing ²³	X														
Hep B ²²	X														
Hep C ²³	X														
CMV ²³	X						X ²³					X ²³			
Serum beta2-microglobulin	X					X	X	X		X			X		
Pregnancy Test ²	X														
Research Blood Samples ⁸	X					X						X ²⁵	X	X ²⁶	
Pathology Review ³	X														
QOL Questionnaire (FACT-Lym)	X					X						X ²⁷	X	X ²⁷	

- Chemistry will include uric acid, phosphorus, LDH and direct bilirubin. See section 7.2 for full list or required labs to be collected.
- A serum pregnancy test for females of childbearing potential must be done ≤ 3 days of treatment start date with single agent ublituximab induction.. A female of childbearing potential (FCBP) is a sexually mature female who: 1) has not undergone a hysterectomy or bilateral oophorectomy; or 2) has not been naturally postmenopausal for at least 24 consecutive months (i.e., has had menses at any time in the preceding 24 consecutive months). Men must agree to use a latex condom during sexual contact with a FCBP even if they have had a successful vasectomy.
- Central review of pathology is required for confirmation of diagnosis. Completion of central pathology review is not required prior to registration for patients; however, confirmation of availability is required prior to enrollment and materials for central review must be submitted within 30 days after registration. Pathology material: H&E stain and IHC slides or a representative FFPE tissue block from initial diagnosis, including additional material for correlative analysis. Please NOTE: the diagnostic H&E slide and IHC slides will be returned after review. In addition, patients whose tissue is not available may still be eligible to go on trial if they choose to have an SOC biopsy prior to treatment.
- PT/INR assessment frequency (for patients on Coumadin) is per investigator discretion to keep within therapeutic range.
- Imaging must be done ≤ 42 days prior to study registration.

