APPENDIX: CONTRACEPTION GUIDELINES AND PREGNANCY

Females Not of Childbearing Potential are Defined as Follows:

Females are considered post-menopausal and not of child bearing potential if they have had 12 months of natural (spontaneous) amenorrhea with an appropriate clinical profile (e.g. age appropriate, history of vasomotor symptoms) or six months of spontaneous amenorrhea with serum FSH levels > 40 mIU/mL and estradiol < 20 pg/mL] or have had surgical bilateral oophorectomy (with or without hysterectomy) at least six weeks ago. In the case of oophorectomy alone, only when the reproductive status of the woman has been confirmed by follow up hormone level assessment is she considered not of child bearing potential.

Contraceptive Guidelines for Females of Child-Bearing Potential:

Females of child-bearing potential, defined as all females physiologically capable of becoming pregnant, must use effective contraception during the study and for 120 days after the last dose of study treatment. Effective contraception is defined as either:

- True abstinence: When this is in line with the preferred and usual lifestyle of the patient. Periodic abstinence (e.g., calendar, ovulation, symptothermal, post-ovulation methods) and withdrawal are not acceptable methods of contraception.
- Sterilization: have had surgical bilateral oophorectomy (with or without hysterectomy) or tubal ligation at least six weeks ago. In case of oophorectomy alone, only when the reproductive status of the woman has been confirmed by follow up hormone level assessment.
- Male partner sterilization (with the appropriate post-vasectomy documentation of the absence of sperm in the ejaculate). For female patients on the study, the vasectomised male partner should be the sole partner for that patient.
- Oral contraception, injected or implanted hormonal methods.
- Use of a combination of any two of the following (a+b):
 - a) Placement of an intrauterine device (IUD) or intrauterine system (IUS).
 - b) Barrier methods of contraception: Condom or Occlusive cap (diaphragm or cervical/vault caps) with spermicidal foam/gel/film/cream/vaginal suppository.

The following are **unacceptable** forms of contraception for females of childbearing potential:

- Female condom
- Natural family planning (rhythm method) or breastfeeding
- Fertility awareness
- Withdrawal
- Cervical shield

Females of child-bearing potential must have a negative serum pregnancy test ≤ 3 days prior to initiating treatment.

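### Inclusion 9 and Schedule of Events footnote 2 disagree, in both directions, on which women need the only scheduled pregnancy test

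*Combined protocol and SAP*

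**What the plan says.** Four parts of the protocol bear on who is tested.

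- **Section 5.1, Clinical/Laboratory item 9 (inclusion 9).** Women of reproductive potential need a negative serum test in the three days before treatment. The exempt group includes women who are "post-menopausal by history - no menses for" at least one year and women with a hysterectomy. The list continues "OR history of bilateral tubal ligation; OR history of bilateral oophorectomy at least six weeks ago) are exempt from pregnancy testing". After oophorectomy alone, hormone levels must confirm the woman's status. Section 5.1 makes its items binding: "each potential subject must satisfy all of the following inclusion criteria".
- **Section 7.4, footnote 2.** The serum test is mandatory for females of childbearing potential. Such a woman is one who "has not undergone a hysterectomy or bilateral oophorectomy; or 2") "has not been naturally postmenopausal for at least 24 consecutive months". Tubal ligation is not mentioned, and oophorectomy carries no six-week or hormone condition.
- **Section 7.3.1.** Screening items, the serum pregnancy test among them, are to be done as Section 7.4 specifies.
- **Appendix on contraception and pregnancy**, which Section 8.4.4 names as the source of the definition. "Females are considered post-menopausal and not of child bearing potential if they have had 12 months of natural (spontaneous) amenorrhea" with a fitting clinical profile, or "six months of spontaneous amenorrhea with serum FSH levels" and estradiol in the stated range. For women of childbearing potential it lists this as a contraceptive option: "Sterilization: have had surgical bilateral oophorectomy (with or without hysterectomy) or tubal ligation at least six weeks ago".

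The schedule's pregnancy-test row has a single entry, at screening. Section 7.2 ties the test to the start of induction, and the list of combination-phase assessments in Section 7.3.4 contains none.

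On contraception, inclusion 10 asks for a highly effective method together with a barrier. The appendix accepts some single methods, such as oral contraception alone.

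**The concern.** Staff who follow inclusion 9 exactly can leave untested a woman for whom footnote 2 makes the test mandatory. Section 14.3 counts any noncompliance with the protocol as a deviation. With only one scheduled test, a woman missed at screening has no scheduled test at any later point.

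The opposite mistake is also possible. Staff who follow footnote 2 alone can skip a test that a binding eligibility criterion demands after a recent or unconfirmed oophorectomy.

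What is at stake is a small gap in a safety check and avoidable eligibility deviations. The efficacy result is not at stake.

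**Working it through.** The plan gives no figure on this point, so the check sets the rules side by side.

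Let M be months since last menses by natural menopause, H hysterectomy, T bilateral tubal ligation and O bilateral oophorectomy. Let O* be an oophorectomy at least six weeks ago and, if it was the only surgery, confirmed by hormone levels.

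- Inclusion 9: test unless M ≥ 12, or H, or T, or O*.
- Footnote 2 with *and* before its second item: test if (neither H nor O) and M < 24.
- Footnote 2 with the printed *or*: test if (neither H nor O) or M < 24.

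| Woman, with no other exempting feature | Inclusion 9 | Footnote 2, *and* | Footnote 2, *or* | Appendix |
|---|---|---|---|---|
| Menstruating, no surgery | test | test | test | test |
| M 6 to <12, no surgery | test | test | test | exempt only with the FSH and estradiol results |
| **M 12 to <24, no surgery** | **exempt** | **test** | **test** | exempt if the clinical profile fits |
| M ≥ 24, no surgery | exempt | exempt | test | exempt if the clinical profile fits |
| **T, M < 24, no H or O** | **exempt** | **test** | **test** | unclear |
| **O under six weeks ago, or alone and unconfirmed, M < 12** | **test** | **exempt** | **test** | test |
| O*, M < 24 | exempt | exempt | test | exempt |
| H alone, M < 24 | exempt | exempt | test | not listed |

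**Which reading of footnote 2.** The printed *or* would require a test after hysterectomy, and also more than 24 months into natural menopause without surgery. Neither can be intended, so *and* is the sensible reading. The first two conflicts hold under both readings; the oophorectomy conflict arises only under *and*.

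**Completeness in the first direction.** Take M at 0, 6, 12, 18 and 30 months and each of H, T and O* as present or absent. That gives 5 × 2 × 2 × 2 = 40 profiles. Six are exempt under inclusion 9 but tested under footnote 2 (*and*): T with M = 0 or 6, and M = 12 or 18 with or without T. All six fall in the two groups named.

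**Does another section settle it?**

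- Section 7.3.1 points to Section 7.4, which favours footnote 2, but it does not withdraw the explicit exemption in inclusion 9.
- Section 8.4.4 points to the appendix, which sides with inclusion 9 at 12 months, adds a six-month route found nowhere else, and leaves ligation unclear.
- No rule of precedence appears in the text provided.

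**Size.** At most one test per woman is in dispute. The Protocol Synopsis caps screening at 30, so 30 is the ceiling. The documents give no data on age, sex mix or surgical history from which to estimate the number.

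**The case against.** The strongest reply is that the protocol can be followed as it stands. An exemption does not forbid a test, and Section 7.3.1 sends staff to the schedule. For the menopause and ligation groups, testing under footnote 2 breaches neither text. That is right, and it is why the matter is minor. It does not remove the conflict: a reader who relies on inclusion 9 has explicit authority not to test, and footnote 2 alone loses the oophorectomy test.

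A reader might infer more than the documents support:

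- *That fertile women go untested.* Women who are clearly fertile are tested under every version. Section 5.2 excludes pregnant women, and Section 8.4.4 withholds drug when pregnancy is suspected.
- *That 24 months is the correct menopause threshold and 12 is unsafe.* Nothing in the documents shows this. Lowering footnote 2 to 12 months would also reconcile the first group, though not the ligation or oophorectomy groups.
- *That women 12 to under 24 months postmenopausal should also use two contraceptive methods.* Inclusion 9 classes them as not of reproductive potential. Imposing that duty is a separate policy choice with a real burden.
- *That Section 7.5 accepts a single contraceptive method.* It gives examples and refers back to Section 5.1. Only the appendix departs from inclusion 10, and meeting inclusion 10 also satisfies the appendix.
- *That this point calls for a test before combination treatment.* None is scheduled, but whether to add one is a separate decision.

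**Conclusion.** The inconsistency is real, runs both ways and is minor. Two groups are exempt under inclusion 9 but must be tested under footnote 2: women 12 to under 24 months from last menses, and women with bilateral tubal ligation under 24 months postmenopausal, in each case without hysterectomy or oophorectomy. One group is tested under inclusion 9 but not under footnote 2: women whose bilateral oophorectomy was under six weeks ago, or was the only surgery and lacks hormone confirmation, with no other exempting feature. This last part assumes the *and* reading of footnote 2; the first two do not.

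The number affected is unknown, cannot exceed 30 and is probably a few; the last is judgement, not a documented figure. Nothing in Section 10 depends on the testing rule, so the primary endpoint, type I error, power and sample size are unaffected.

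**What to change.** For the screening test, do a serum pregnancy test whenever either inclusion 9 or footnote 2 requires it. In practice, exempt only women with:

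1. a hysterectomy;
2. a bilateral oophorectomy at least six weeks ago, confirmed by hormone levels if it was the only surgery; or
3. at least 24 consecutive months of natural menopause.

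This wording also tests a rare woman whom both texts now exempt, for example one with a recent oophorectomy and an earlier ligation. That is an acceptable price for a simple rule.

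Change *or* to *and* before the second item of footnote 2, and have inclusion 9, footnote 2 and the appendix share this one rule. Word it as a rule about who is tested, so that it does not by itself extend contraception duties to women 12 to under 24 months postmenopausal. Separately, state that the two-method requirement in inclusion 10 governs where the appendix accepts one method.

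Staff can apply the testing rule at once, since it breaches neither text. Instructing them to follow footnote 2 alone would not do, because it drops the oophorectomy test.

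The cost is at most one extra serum test per woman at screening and a wording amendment, which under Section 13.2 needs approval from the drug supplier and the IRB. Visits, sample size and analysis do not change, and no test is added before combination treatment.

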7.5 CONCOMITANT MEDICATIONS, TREATMENTS, AND PROCEDURES

All concomitant prescription medications taken during study participation will be recorded on the case report forms (CRFs). For this protocol, a prescription medication is defined as a medication that can be prescribed only by a properly authorized/licensed clinician. Medications reported in the CRF are concomitant prescription medications..

In addition, examples of acceptable methods of contraception include the following (also listed in section 5.1):

- Bilateral tube ligation
- Male sterilization
- Hormonal contraceptives that inhibit ovulation
- Hormone-releasing intrauterine devices
- Copper intrauterine devices

NOTE: Periodic abstinence (e.g. calendar, ovulation, symptothermal, or post-ovulation methods) and withdrawal are NOT acceptable methods of contraception.

7.5.1 PRECAUTIONARY MEDICATIONS, TREATMENTS, AND PROCEDURES

- Antiemetics may be used at the discretion of the attending physician.
- Tumor lysis syndrome prophylaxis will be used at the discretion of the treating physician.
- Blood products and growth factors should be utilized as clinically warranted and following institutional policies and recommendations. Growth factors should not be used to meet eligibility criteria. Pegfilgrastim support may be given during therapy. Treat as needed.
- Patients should receive full supportive care while on this study. This includes blood product support, antibiotic treatment, and treatment of other newly diagnosed or concurrent medical conditions.
- All blood products and concomitant medications such as anti-diarrheals, analgesics, and/or antiemetics received from the first day of study treatment administration until 30 days after the final dose of study treatment will be recorded in the medical records.

7.6 PROHIBITED MEDICATIONS, TREATMENTS, AND PROCEDURES

The following medications are **prohibited** while on study treatment (exceptions noted):

- Treatment with immuno-suppressive **medications (except as used to treat drug-related adverse events)** will not be permitted unless discussed with and approved by the study principal investigator. This will be documented in the EMR system.
- Patients will also not be allowed to be treated with any concurrent anti-neoplastic therapy, including chemotherapy, non-palliative radiotherapy, and Chinese medications used for cancer treatment.

Treatment needs to be administered in collaboration with an oncology-trained pharmacist. Drugs that interact with ublituximab and umbralisib should be used with caution or avoided as per institutional guidelines.

7.7 PROPHYLACTIC MEDICATIONS, TREATMENTS, AND PROCEDURES

- Prophylactic medications, treatments and procedures should be performed according to institutional guidelines. This includes prophylactic antibiotics, anti-fungals, or PJP prophylaxis.
- Topical, inhaled, articular, intra-nasal corticosteroids are permitted. A brief (<3 weeks) course of steroids is permitted for purposes of prophylaxis (e.g. contrast) or treatment of non-auto-immune conditions (e.g. anaphylaxis).
- Patients receiving umbralisib are required to start prophylaxis treatment with pneumocystis jiroveci pneumonia (PJP) and antiviral therapy prior to Day 1 of Cycle 1 of combination treatment.
 - Anti-viral Prophylaxis: Valtrex 500 mg daily or Acyclovir 400 mg BID or equivalent.
 - PJP Prophylaxis: Dapsone 100 mg daily. Other acceptable options include trimethoprim-sulphamethoxazole twice a week, atovaquone, or inhaled pentamadine.
- Final choice of PJP and anti-viral prophylactic therapy is per investigator discretion.
- If PJP or anti-viral therapy is not tolerated, alternate to a different PJP or anti-viral therapy, discontinue, or reduce dose/schedule as per Investigator Discretion.
- Prophylaxis with an antiviral agent effective against hepatitis B is required in subjects with a prior known history of hepatitis B and for those with a positive antiHBc with negative HBsAg at screening.
- Promptly consult clinicians with an expertise in managing subjects with a prior history of hepatitis B regarding monitoring and consideration of options for hepatitis B antiviral therapy for prophylaxis/treatment.

7.8 RESCUE MEDICATIONS, TREATMENTS, AND PROCEDURES

Patients with adverse events while on study drug should be treated as indicated in section 6 of protocol. Other medical conditions that arise while patients are on study should be treated according to standard of care. The principal investigator should be made aware of serious adverse events occurring while patients are on study. Inquiries regarding handling of adverse events occurring while on study that are not described in this protocol should be directed towards the principal investigator.

